This study is designed as a prospective, double arm, study. Patients with a diagnosed rupture of the anterior cruciate ligament (ACL) who are scheduled for surgical reconstruction will be considered for enrollment. Eligible subjects will be allocated to one of two groups based on the location of the tibial tunnel (anterior vs. posterior) during the surgical procedure. The study population will consist of patients 16-50 years of age, with ACL rupture, who are seeking surgical reconstruction. Patients with active infection, previous ACL surgery, multiple ligament knee injury, previous joint modifying surgery in target knee within 12 months of planned procedure, flexion contracture, valgus alignment, pathologic ligament instability, knee osteoarthritis, inflammatory joint disease, metabolic bone disease (marked bone loss or moderate to severe osteoporosis), comorbidities such as type 1 diabetes, connective tissue disorder, or morbid obesity (BMI ≥35) will be excluded.

Subjects will return for follow-up visits at 6, 12, and 24 months post-surgery. If a subject is unable to come to UVA for a follow up visit, a home visit can be arranged with a member of the study team. Note that all data cannot be collected through a home visit, but instead only the subjective outcomes and some aspects of the knee exam can be collected. Follow up will be completed at 24 months for all enrolled subjects. Additionally, subjects with a prior ACL reconstruction who meet all study criteria, may enter the study at any post-operative time point (retrospective aspect of the study).

The primary objective of this study is to collect data on subjective and objective measures of knee related function in subjects with an anterior vs. posterior placed tibial tunnel through 24 months postoperative follow-up.

The primary analysis will compare groups at 24-months post-op with regard to:

- 1. Clinically significant difference of at least 8 points on IKDC score
- 2. Clinically significant difference of at least 2.4 mm knee joint laxity (KT-1000)

Background

1. Provide the scientific background, rationale and relevance of this project.

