Although extensive research has been carried out on ACL Femoral Tunnel placement, very little attention has been given to the tibial tunnel. Staubli et al. suggest that the tibial tunnel be placed in the center of the ACL footprint, which they described as being approximately 43% of the way (anterior to posterior) across the proximal tibia at its widest extent. However, others have suggested that a more anterior placement may yield improved biomechanical and clinical results. The center of the ACL footprint and the posterior aspect of the anterior horn of the lateral meniscus does not yield tibial tunnel placement a consistent percentage of the way across the tibial plateau⁴, therefore, guidelines should be based on intraoperative fluoroscopic measurements. However, the question remaining is what percentage of the A-P distance across the tibia is the ideal location for the tibial tunnel in ACL reconstruction. This study will help answer that question.

Page 4 of 41

Hypothesis to be Tested

Objective:

Compare anterior versus posterior tibial tunnel placement for ACL reconstruction in a prospective randomized clinical trial.

Hypotheses:

A more anterior placed tibial tunnel will yield improved outcomes with regard to:

- 1. Improved knee-specific self-reported function (IKDC)
- 2. Decreased knee joint laxity (KT-1000)

Study Design: Biomedical

- 1. Will controls be used? No
- 2. What is the study design?

Single-blind, randomized controlled clinical trial

3. Does the study involve a placebo? No

Human Participants

Ages: 16-50

Sex: Male and Female

Race: All

Subjects- see below

INSTRUCTIONS: For question 1-4 below insert an exact #. Ranges or OPEN is not allowed. This # should be the maximum # you expect to need to enroll (i.e. sign consent) If you are only collecting specimens the number of participants should equate to the # of specimens you need. If you are collecting only data from a chart review the number should designate the number of subjects whose medical records you plan to review. Age/ Sex/Race criteria should designate the demographics of participants from whom you will obtain the specimen/data.

- **1.** Provide target # of subjects (at all sites) needed to complete protocol.75(prospective aspect) 45 for retrospectice (UVA only)
- 2. Describe expected rate of screen failure/ dropouts/withdrawals from all sites.

We expect up to a 20% rate of attrition due to loss of follow up.

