- 3. How many subjects will be enrolled at all sites? 90- prospective, 45-retrospective (UVA only)
- **4.** How many subjects will sign a consent form under this UVa protocol? Between Jordan-Young Institute and UVA up to 90 subjects will sign consent for the prospective portion of the study—N=55 at UVA. 45

Page 5 of 41

subjects will sign a consent form for the retrospective portion of the study at UVA only. Total of 100 subjects will sign a consent form under this UVA protocol.

5. Provide an estimated time line for the study.

Enrolled subjects will be followed for 2 years post-surgery, or up until 2 years post-operatively for those who enter the study after surgery. We expect 50% enrollment to be achieved within one year, and 100% in two years. We would anticipate completion of follow up to occur in four years.

Inclusion/Exclusion Criteria

INSTRUCTIONS:

The inclusion and exclusion criteria should be written in bullet format.

If this is a collection of only retrospective* specimens or data, the inclusion criteria must include a start and stop date for when specimens/ data will be collected.

The stop date must be prior to the version date of this protocol.

*Retrospective: all specimens are in a lab at the time this protocol is approved by the IRB. All data exists in medical records or records from previous studies at the time this protocol is approved by the IRB.

1. List the criteria for inclusion

- Age at time of randomization or initial surgery: 16 50 years (skeletally mature)
- Primary, uncomplicated ACL reconstruction
- Autograft (STG or BPTB)

2. List the criteria for exclusion

- Multiple ligament knee injury (full thickness)
- Revision ACL reconstruction
- ACL reconstruction with allograft
- Meniscectomy > 75%
- Treatable articular cartilage lesions (debridement acceptable)
- Diagnosis of tibiofemoral or patellofemoral osteoarthritis (Kellgren Lawrence grade > II)
- Valgus knee alignment (weight bearing line outside of joint center)
- Prior ligament reconstruction of cartilage repair surgery in either ankle, knee, or hip
- Prior arthroscopic debridement surgery in either ankle, knee, or hip within 12 months
- Clinical evidence of hip disease
- Patellofemoral joint instability
- Significant patellar or tibiofemoral mal-alignment
- BMI > 35
- Type 1 Diabetes Mellitus
- Known connective tissue disorder (e.g. Ehlers-Danlos)
- Peripheral neuropathy
- Neurovascular/ circulatory disorder

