- Any form of inflammatory arthritis (e.g. RA, gout, pseudogout, lupus, etc.)

Page 6 of 41

- Significant co-morbid conditions as determined by the investigator (e.g. malignancy, renal, hepatic disease, etc.)
- Known or suspected psychological disorder
- 3. List any restrictions on use of other drugs or treatments. N/A

Statistical Considerations

1. **Is stratification/randomization involved?** Yes.

► IF YES, describe the stratification/ randomization scheme.

Block randomization will be completed *a priori* via a random number generator. 20 subjects will be allocated to group within each block (10 per group). Group assignments will be sealed in an opaque envelope each containing a number from 001-090. Each subject will be randomly assigned in a 1:1 ratio to receive one of the treatments (group) described below. Randomization envelope #001 will be used for the first subject, #002 for the second and so on. Group assignment for enrolled subjects will be determined intra-operatively. Prior to the determination of group assignment, the treating surgeon will drill two tibial tunnel guide pins, assessing pin placement via fluoroscopy, to ensure that one tunnel is anterior and the other is posterior to the 35% line. The sealed envelope will then be opened following confirmation of guide pin placement, and the procedure will be performed in accordance with the randomized group assignment.

Patients with a prior history of ACL reconstruction who enter the study post-operatively will be assigned to the appropriate group based on graft placement (anterior or posterior) that was performed for clinical care.

► IF YES, who will generate the randomization scheme?

X Other: Study coordinator

2. What are the statistical considerations for the protocol?

We have designed the study in a way that will make it easy to match an appropriate statistical procedure to test our primary hypotheses. Subjective and objective measures of knee function will be evaluated at 6, 12 and 24 months post-surgery.

3. Provide a justification for the sample size used in this protocol.

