APPENDIX: Recruitment

Recruitment includes identifying, review of records to determine eligibility or any contact to determine a potential subjects interest in the study.

*The UVa HIPAA covered entity is composed of the UVa VP Office of Research, the Health System, School of Medicine, School of Nursing, Nutrition Services (Morrisons), the Sheila C. Johnson Center, the Exercise and Sports Injury Laboratory and the Exercise Physiology Laboratory.

1. How do you plan to identify potential subjects?

- To "identify" a potential subject refers to steps you plan to take to determine which individuals
 would qualify to participate in your study. This does NOT include steps to actually contact those
 individuals.
- If your study involves more than one group of subjects (e.g. controls and cases or subjects and caregivers) note below which groups are being identified by the given method.
- Check the methods you plan to utilize:
- a.__X__ Chart Review/ Clinic Schedule Review/ Database Review from a database established for health care operations (departmental clinical database) or an Improvement Project (e.g. Performance Improvement, Practice Improvement, Quality Improvement).
 If you plan to obtain data from the UVa Enterprise Data Warehouse (EDW) please see option b below.

DHHS: Study team requests Waiver of Consent to identify potential subjects.

HIPAA: Allowed under Preparatory to Research if PHI to be accessed.

IMPORTANT

Keep in mind that PHI in the medical record may only be accessed by individuals who work under the UVa HIPAA covered entity; which means they meet one of the following criteria:

- --a UVa student working in the UVa HIPAA Covered Entity*
- --a faculty or staff member in a PAID appointment in the UVA HIPAA Covered Entity*

b__X_ Review of a database that was established to keep data to be used for future research such as the CDR, departmental research database or use of data from a separate current active research protocol.

If you plan to obtain data from the UVa Enterprise Data Warehouse (EDW) you are required to submit your request to the CDR. The CDR staff will work with the EDW to obtain the data you need.

DHHS: Study team requests Waiver of Consent to identify potential subjects.

HIPAA: Allowed under Preparatory to Research if PHI to be accessed.

IMPORTANT

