Keep in mind that PHI in the medical record may only be accessed by individuals who work under the UVa HIPAA covered entity; which means they who meet one of the following criteria:

- --a UVa student working in the UVa HIPAA Covered Entity*
- --a faculty or staff member in a PAID appointment in the UVA HIPAA Covered Entity*

The information from which you are obtaining potential subjects must also have an IRB protocol approval. If this item is checked, enter the IRB # below.

IRB# 10797

If obtaining information from the Clinical Data Repository (CDR) insert IRB # 10797

c. _X__ Patients UVa health care provider supplies the UVa study team with the patients contact information without patients' knowledge.

DHHS: Study team requests Waiver of Consent to identify potential subjects.

HIPAA: Allowed under Preparatory to Research if PHI will be shared by the health care provider.

IMPORTANT

Keep in mind that PHI may only be given to individuals who work under the UVa HIPAA covered entity; which means they meet one of the following criteria:

- --a UVa student working in the UVa HIPAA Covered Entity*
- --a faculty or staff member in a PAID appointment in the UVA HIPAA Covered Entity*
- d. X Patient obtains information about the study from their health care provider. The patient contacts the study team if interested in participating. (Health care provider may or may not also be the a member of the study team)

DHHS: NA

HIPAA: Allowed under Health Care Operations

If this choice is checked, check 3d-INDIRECT CONTACT below.

e. _X__ Potential subjects will not be directly identified. They will respond to an advertisement such as a flyer, brochure etc.

If this choice is checked, check 3d- INDIRECT CONTACT below.

DHHS & HIPAA: NA

f. Potential subjects have previously signed a consent to have their name in a registry/database to be contacted for future studies of this type.

IRB# of registry/ database:

DHHS & HIPAA: NA

If item # a, b or c is checked above and if this protocol involves the use of protected health information do you confirm the following to be true?

- The use or disclosure is sought solely to review protected health information as necessary to prepare the research protocol or other similar preparatory purposes.
- No PHI will be removed from the UVa covered entity.
- The PHI that the researcher seeks to use or access is necessary for the research purposes.

Yes

2. How will potential subjects be contacted?

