APPENDIX: Clinical Data Repository

1. Will you be obtaining data from the UVa Clinical Data Repository (CDR)? Yes

INSTRUCTIONS:

► If YES, check the categories of data elements below that you plan to obtain from the CDR. You are advised to talk to CDR personnel prior to completing this section.

CATEGORY	DATA ELEMENTS	CHECK ALL THAT APPLY
Demographics	e.g. Gender, race, age	X
Administrative e.g. Includes payor, payscale, length of stay, fact of visits (inpatient or outpatient), locations of service (inpatient or outpatient), providers		

Financial	e.g. Charges or costs associated with care	
	e.g. Diagnoses	X
	e.g. Procedures	X
	e.g. Mortality	
	e.g. Laboratory / Microbiology	
Clinical Data	Results	
	e.g. Medications	
	e.g. Vitals, Height / Weight, Other	X
	Clinical Parameters	
	e.g. Other (specify)	
	e.g. Includes discharge summaries,	X
Narrative Reports	pathology reports, operative notes,	
	etc.	

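### No consecutive list, operation-date window or screening log governs entry of the 45 non-randomised post-operative patients, so referral can depend on tunnel position and interim result

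*Combined protocol and SAP*

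**What the plan says.** **Who the cohort is.** The opening study summary says that patients with a prior reconstruction who meet the criteria "may enter the study at any post-operative time point (retrospective aspect of the study"). The Subjects section, item 3, gives the numbers as "90- prospective, 45-retrospective (UVA only"). Under Statistical Considerations, item 1, these patients are not randomised. They are put in a group by the "graft placement (anterior or posterior) that was performed for clinical care".

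**How they may be found.** Appendix: Recruitment, item 1, tells the study team to "note below which groups are being identified by the given method". Routes a (chart, schedule or clinical database review), b (research database, with the Clinical Data Repository protocol number entered), c ("Patients UVa health care provider supplies the UVa study team with the patients contact information"), d (the patient hears from the provider and contacts the team) and e ("They will respond to an advertisement such as a flyer, brochure etc") are all checked. No group is named against any of them. Item 2, on contact, carries the same instruction. Its routes a to d are checked, again with no group named.

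**What is not there.** The plan sets no operation-date window, consecutive series, sampling frame or log of patients not approached for this cohort.

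**What the analysis does.** Statistical Considerations, item 4, plans independent t tests at each time point. It does not say whether the 45 are pooled with the randomised patients. Item 7(d), on differences between sites, mentions unspecified later measures to account for patient characteristics and demographics.

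**The concern.** For a patient not yet operated on, the recruitment route cannot depend on the result of the operation. For a post-operative entrant it can. A provider who did the operation and saw the patient afterwards may know the tunnel position and how the knee is doing when deciding whether to pass on a name. Under route d that provider may be a member of the study team, and contact route c lets team members approach their own patients.

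The two kinds of selection have different consequences:

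- If entry depends on tunnel position and result together, a difference between groups can be created or reversed.
- If entry depends on result alone, and equally in both groups, there is no false difference when the truth is zero, but a real difference is shrunk.

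Adjusting for demographics addresses neither, because the driver of entry is the result itself. Without a list of everyone eligible, the extent of selection could not be judged afterwards.

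**Working it through.** **Inputs from the plan.** IKDC SD 12 and target difference 8 points (Statistical Considerations, item 3); 90 prospective patients, 45 post-operative patients and 20% attrition (Subjects section, items 2 and 3).

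**Cohort size.** The plan's own counts agree: 55 prospective consents at UVA + 45 post-operative = 100, the total stated in item 4. The cohort is 45/(90 + 45) = 33% of planned patients. After 20% attrition in the randomised part, 90 × 0.8 = 72 remain. Pooled totals are therefore 72 + 45 = 117 up to 90 + 45 = 135. The completion target of 75 in item 1 lies inside the 72 to 90 range.

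**Assumptions (not in the plan).** Normal scores, an even tunnel split in the cohort, two-sided 5% test, selection acting directly on the analysed score.

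**1. One-arm selection, no true difference.** If the lowest fraction p of one arm never enters, that arm's mean rises by 12 × φ(z_p)/(1 − p).

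- p = 10%: 12 × 0.1755/0.90 = 2.34 points, or 29% of the 8-point target.
- p = 25%: 12 × 0.3178/0.75 = 5.08 points, or 64%.

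Pooled bias = cohort bias × 45/N. Standard error = 12 × √(2/(N/2)). Type I error comes from the normal approximation with shift bias/SE.

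| Analysis | SE | Bias, 10% / 25% | Type I error, 10% / 25% |
|---|---|---|---|
| The 45 alone (22.5 per arm, noncentral t) | 3.58 | 2.34 / 5.08 | 10% / 28% |
| Pooled, N = 117 | 2.22 | 0.90 / 1.96 | 7% / 14% |
| Pooled, N = 135 | 2.07 | 0.78 / 1.69 | 7% / 13% |

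**2. Result-only selection, true difference 8.** If patients in both arms below the posterior arm's 10th or 25th percentile do not enter, the difference within the cohort is 6.40 or 5.06 points. Pooled, it is 8 − (8 − 6.40) × 45/N = 7.4 to 7.5, or 8 − (8 − 5.06) × 45/N = 6.9 to 7.0.

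**3. Does covariate adjustment help?** A simulation with no true effect let entry depend on position and score together, with log-odds of 0.25, 0.5 or 1 per SD and opposite sign by group. One measured covariate explained 25% of IKDC variance.

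- Cohort difference: 2.8, 5.6 or 9.6 points.
- After adjustment: 2.1, 4.2 or 7.6 points, so only about a quarter or less of the bias was removed.
- Type I error pooled with 72 randomised patients, unadjusted: 7%, 16% or 38%.
- In the randomised patients alone the mean difference stayed at zero.

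**4. Why these are upper bounds for a given strength of selection.** The primary comparison is at 24 months, and post-operative entrants complete the visits that remain after entry. What a provider or patient can usually know at entry is an interim result. If that result has correlation ρ with the 24-month score, the bias in step 1 is multiplied by ρ.

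**The case against.** The strongest reply is that the link to this cohort rests on a blank. The recruitment appendix never mentions the post-operative patients, and its request for group labels is generic form text. Routes a and b are checked too, and either could supply a systematic list. All of this stands. A reader might infer that referral and flyers replace a list, or that the 45 are in fact recruited that way. The documents say neither. They leave routes c to e open and do not require a list.

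Three further limits also stand:

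- A reader might infer that the outcome is already known when these patients enter. The 24-month measurements are generally taken after entry, so selection acts on an earlier and imperfect guide to them.
- The routes differ. The plan keeps group assignment from participants, though it does not say how this applies to someone operated on earlier. A flyer reply therefore selects mainly on result. One-arm selection fits provider referral, not route e.
- A reader might take 28% as the trial's false-positive rate. It describes the 45 tested alone, an analysis that the plan does not state.

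Nor is it right that the bias could never be removed. Weighting could work if the drivers of entry were recorded, but no such recording is planned. Analysing the randomised patients alone keeps the bias out of that comparison. It does not protect any result that uses the 45.

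**Conclusion.** The point holds as a gap in the sampling frame. All five routes are open, no group is named, and no consecutive list, date window or log is required for a non-randomised cohort whose tunnel position is already fixed and whose interim result may be known. Selection on both is possible, the adjustment mentioned in the plan would not correct it, and its extent could not be assessed.

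The size depends on assumed selection, since the documents give no data on it. With the lowest 10% or 25% of one arm missing, the upper bound is 2.3 or 5.1 IKDC points within the cohort. Pooled, it is about 0.8 to 0.9 or 1.7 to 2.0 points, with type I error about 7% or 13 to 14%. The pooled figures matter only if the 45 join the main comparison, which the plan leaves unstated. The change should be made, because it is cheap and the loss of information cannot be repaired later.

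**What to change.** In Appendix: Recruitment, items 1 and 2:

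- State that identification routes c, d and e, and indirect contact, apply only to patients recruited before surgery.
- Identify post-operative entrants only through routes a and b, from a Clinical Data Repository list of all UVA primary autograft ACL reconstructions in a fixed operation-date window.
- Draw up the list before follow-up results are reviewed, and invite patients in order of operation date.
- Report the numbers listed, eligible, invited, declined and entered, by tunnel group.

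In Statistical Considerations, state that the randomised comparison will also be reported without the 45.

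**Cost.** Mostly wording. Access to diagnoses, procedures and narrative reports, including "pathology reports, operative notes", is already requested in Appendix: Clinical Data Repository. Eligibility will probably have to be judged from operative notes that may also show tunnel position, so the order of these steps needs a short written procedure. The cohort may fill more slowly or stop short of 45.

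**What it does not do.** It reduces selection at referral and makes non-response countable. Patients can still accept or decline according to how the knee feels, and the tunnel was still chosen in clinical care, so confounding remains. That is why the separate randomised result is needed.
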